3.0 Safety net procedures for between therapy and follow up time points

- 3.1 All participants will be offered a *Contact Card* at the point of randomisation. This will list the contact details of services to call 24/7 if they feel they need to talk with someone about their mental health outside of their therapy session and throughout their trial participation. Contact details will include Lifeline, Samaritans, their GP and where appropriate their Aftercare case worker and Inspire's 24/7 helpline.
 - 3.1.1 For participants in therapy, the therapist will record participant self-reports of all contacts being made in the therapy safety log.
 - 3.1.2 For participants in follow up, the researcher will note such self-reports in the data collected and ask the participant for details. Details, if provided, will be recorded in the researcher's participant safety log.
 - 3.1.3 The unblinded researcher will review the therapy database weekly to determine if any activity has been logged in the previous 7 days.
- 3.2 The RTM therapy is experimental and, in contrast to TF-CBT, does not carry evidence of treatment effects and safety issues. Therefore an additional participant safety feature is provided for this group and their family members. An additional contact number for an Independent Clinical Psychologist (ICP) will be provided.
- 3.3 The ICP is funded for ½ an hour a week for any RTM participant or their family member to contact them by telephone with concerns for participant mental health safety and or vulnerable adult and or safeguarding concerns.
- 3.4 Where the ICP identifies a need to escalate their concern regarding either the mental health care or safeguarding and vulnerable adult of a participant and or their immediate family member they will take action themselves and encourage the participant to take action. These actions are specified as:
 - 3.4.1 Advise the participant to make contact with their GP
 - 3.4.2 Advise the participant to contact a family member
 - 3.4.3 Where possible the ICP will speak with a family member to signpost them to the GP for escalation
 - 3.4.4 The ICP will independently inform the participant's GP within 2 hours to alert them to the participant's need for mental health escalation and safeguarding.
 - 3.4.5 If the participant is still in therapy they will inform and update the participant's Inspire therapist within a minimum of 24-hours and in advance of the next scheduled therapy session
 - 3.4.5.1 The therapist will inform the named researcher3.4.6 If the participant has completed or dropped out of therapy early (unplanned
 - ending) with Inspire and are in follow-up they will inform the named researcher
 - 3.4.7 They will keep a log of the incident, the clinical concerns noted and the actions taken.
 - 3.4.8 The ICP will have weekly email contact with the named researcher to report any safety logs and or safeguarding concerns in the previous 7 days.
- 3.5 The ICP will have independent access to the Data Monitoring and Ethics Chair (DMEC) chair to whom they will report any serious adverse events.

4.0 Care escalation procedures in the case of adverse event

- 4.1 If at point of referral or during the course of treatment, Inspire therapists become concerned about the welfare of any participant or immediate family member they will escalate their concerns through Inspire's standardised risk assessment, escalation, management and safeguarding policies and procedures. Where necessary they will contact the participant's GP to mobilise referral to crisis response, NHS primary or secondary care. Likewise, if a safeguarding and vulnerable adults concern is identified this will be escalated, acted on and reported to the relevant statutory body safeguarding team.
 - 4.1.1 The PCL- 5 along with Core-10 will be completed at each therapy session. If ≥10 point rise in PCL-5 score occurs since the previous therapy session, or 15 point rise from baseline, or the maximum score of 80 is recorded on the PCL-5 alongside an escalation in risk "flagged" using CORE-10, they will use their clinical judgement to assess whether escalation is appropriate.
 - 4.1.2 Any ≥10 point rise in PCL-5 score that occurs since the previous therapy session, or 15 point rise from baseline, or the maximum score of 80 is recorded on the PCL-5, will be detected by the unblinded member of the research team who will inform the DMEC chair within 3 working days.
- 4.2 If a participant's PCL-5 score rises by ≥10 points from the previous follow up, or 15 point rise from baseline, or the maximum score of 80 is recorded on the PCL5, the unblinded researcher will make contact with the participant within six hours of noting the rise in score and encourage them to contact their GP and/or their case worker. They will advise the participant that the researcher will need to contact the participant's case worker (or GP if no case worker) to alert them to the rise in PTSD symptoms.

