3.11 Interventions

3.11.1 Therapy A: Experimental Group – RTM Protocol

The experimental intervention is the Reconsolidation of Traumatic Memories protocol (RTM), an NLP based, non-traumatising intervention (28, 31-33) delivered in up to 5 x 90 -120 mins weekly sessions by a single trained therapist. The RTM Protocol is a brief cognitive intervention with minimal and non-traumatizing exposure to the original stimulus. The RTM protocol effectively rewrites the emotional elements of the memory by taking advantage of the phenomenon of reconsolidation (51, 52). The procedure is manualized and fully described by Gray & Liotta (2012)(53). Reconsolidation describes the reactivation of long term, otherwise permanent memories, by their evocation in certain contexts. When a memory is reactivated, it labilises, that is, it becomes subject to change. If the circumstances surrounding the memory remain the same, the memory remains unchanged; it is maintained in its current state. If circumstances have intensified, the impact of the memory may become worse; retraumatization can add to the intensity of trauma memories. If the new circumstance provides evidence that a threat of negative emotional stimulus is no longer relevant, the strength of the affective charge may decrease.

The intervention proceeds as follows:

- 1. Evoke the trauma, with or without description (most NLP interventions can be completed content free).
- 2. Interrupt the re-emergence of the trauma as soon as the client begins to show physiological signs of its onset. Changes in breathing, skin colour, posture, pupil dilation and eye fixation are typical signs of memory access. As they appear, the state is to be broken by reorienting the client to the present, by changing the subject, redirecting their attention into a different sensory system, or firing off a pre-existing anchor. However it is accomplished, it is important to stop the development of the symptoms before they take control of the client's consciousness.
- 3. After a few minutes away from the trauma, ask the client to think of a time before the trauma when they were doing something pleasant in a safe, neutral context.
- 4. Instruct the client to imagine that they are sitting in a movie theatre and that they are watching that scene on the screen.

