3.11.2 Therapy B: Comparison Group – TF-CBT

Trauma-Focused Cognitive Behaviour Therapy delivered over up to 18 x 60-90 minute weekly sessions delivered by a single TF-CBT trained therapist (15). TF-CBT is the gold standard for treating PTSD and is currently the first line of treatment recommended by NICE for PTSD (15). Research evaluating TF-CBT in adults with PTSD has established an empirical base supporting the efficacy of the intervention(19, 54, 55). A substantial number of RCTs in England and Northern Ireland have established the efficacy of TF-CBT in PTSD(56-59). These RCTs have shown very large effect sizes in treating PTSD symptoms and associated symptoms of depression and anxiety. TF-CBT for PTSD is a face-to-face therapy of up to 12 x 60 to 90-minute sessions that involves identifying the relevant appraisals, memory characteristics and triggers, and behavioural and cognitive strategies that maintain PTSD symptoms.

The cognitive model of PTSD developed by Ehlers and Clark (2000) (60) will be the model used in this study as it displays the largest treatment effect sizes and significant symptom improvements (56, 57, 61) suggesting why it is widely carried out and recommended in IAPT services (62, 63). This cognitive theory of PTSD addresses these symptoms by:

(A) modifying excessively negative appraisals of the trauma and/or its sequelae in maintaining the symptomatology of PTSD,

(B) reducing re-experiencing by elaboration of the trauma memories and discrimination of triggers in the development of PTSD, and

(C) dropping dysfunctional behaviours and cognitive strategies, particularly those related to avoidance of triggers for intrusive symptoms.

These are strategies that have the immediate aim of reducing one's sense of current threat but have the long-term effect of maintaining the disorder and are common in PTSD.

TF-CBT in this study will be delivered in up to 18 x 60 to 90-minute sessions each as recommended by NICE. The course and delivery of TF-CBT in this study for veterans with simple PTSD proceeds as follows (for complex PTSD, the same delivery may take up to 18 sessions):

Session 1:	Treatment goals
	Normalisation of PTSD symptoms
	Identification of main intrusive memories
	• Initial identification of maintaining factors (appraisals, cognitive strategies
	such as thought suppression, rumination, hypervigilance, safety
	behaviours) and initial shared case formulation (to be revised throughout
	treatment)

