1.0 Lines of responsibility and accountability

- 1.1 From the point at which a potential participant is handed over to Inspire for eligibility assessment through to the point of discharge, Inspire have responsibility and clinical governance accountability for the participant's mental health and wellbeing and including their own safety and where relevant the safety of others and including the safeguarding of children and vulnerable adults.
- 1.2 From the point of discharge from Inspire therapy to the point of 52 week follow, up or withdrawal from the trial, the participant's GP holds responsibility and accountability for the participant's mental health and wellbeing and this includes their safety.
- 1.3 Participant safety will be a standing agenda item on every fortnightly King's- QUB research team meeting.
- 1.4 Data Monitoring and Ethics Committee (DMEC) will meet four times during the trial comprising three trauma experts, a veteran welfare expert and an independent statistician. The DMEC terms of reference will operate according to the King's Clinical Trials Unit Standard Operating Procedures. The research team will report any participant safety issues to the DMEC within 48 hrs of each fortnightly King's and Queen's meeting.

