2.0 Definitions related of safety

- 2.1 Mental health safety symptom severity, deterioration is assessed using the PCL-5 selfreport screening questionnaire (39, 67, 68) completed by the participant at the beginning of every therapy session until discharge. Any existing or emergent safeguarding and or vulnerable adult concern will be assessed and monitored at each session with proportionate action taken in accordance with legislative reporting requirements.
- 2.2 Mental health safety is assessed using the PCL-5 self-report screening questionnaire completed by the participant at the following time points following discharge; 6 weeks post randomisation which is likely to be post discharge in the RTM group and during therapy in the TF-CBT group; 12 weeks post randomisation; 20 weeks post randomisation and 52 weeks post randomisation.
 - 2.2.1 The named researcher will review all incoming follow up PCL-5 scores within 72 hrs of receipt.
- 2.3 PTSD Adverse Events are defined as a ≥10 point rise in the self-report PCL-5 since the previous therapy session or a 15 point rise from baseline or the maximum score of 80 being reached and/or relapse into alcohol and/or substance misuse at a hazardous level which integrated with the clinical judgement of the treating therapist will determine the action taken
- 2.4 PTSD Serious Adverse Events are defined as hospital admission for mental ill-health, selfharm, suicide and attempted or completed suicide.

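### Appendix 1 item 4.2 does not send a follow-up PCL-5 rise to the Inspire therapist, although the week 6 and week 12 questionnaires can fall during therapy

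*Protocol*

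**What the plan says.** Item 4.2 of Appendix 1 is triggered by a PCL-5 rise of at least 10 points since the previous follow-up, a rise of 15 points from baseline, or a score of 80. The unblinded researcher contacts the participant within six hours of noting the rise, is to "encourage them to contact their GP and/or their case worker", and tells the participant that the case worker will be alerted, or the GP if there is no case worker. No other clinician is named, and the item is not restricted to discharged participants. Under item 2.2.1 the named researcher "will review all incoming follow up PCL-5 scores within 72 hrs of receipt".

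Item 1.1 says that from handover "through to the point of discharge, Inspire have responsibility and clinical governance accountability". Item 1.2 passes accountability to the GP only after discharge. Item 2.2 introduces its list of time points as coming after discharge, but describes the first as "6 weeks post randomisation which is likely to be post discharge in the RTM group and during therapy in the TF-CBT group".

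TF-CBT is "delivered over up to 18 x 60-90 minute weekly sessions" (section 3.11.2) and RTM is "delivered in up to 5 x 90 -120 mins weekly sessions" (section 3.11.1).

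**The concern.** The recipients in item 4.2 suit someone who has left therapy. For someone still in therapy, the accountable clinician is at Inspire, and that clinician is the one left out. Reading item 4.2 as applying only after discharge does not solve this: a rise on a questionnaire completed during therapy would then prompt no contact at all under that item.

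The protocol draws the missing distinction elsewhere. Under item 3.4.5 the independent clinical psychologist must inform the Inspire therapist if the participant is still in therapy, before the next session and with a 24-hour limit (the item says a minimum of 24 hours, which I read as an upper limit). Item 3.4.6 deals separately with people who have left therapy. That psychologist serves RTM participants only (items 3.2 and 3.3). TF-CBT, the arm more likely to be in therapy at weeks 6 and 12, has no equivalent.

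At stake is a delay before the responsible clinician learns of a deterioration. Section 3.1 lists understanding safety risks as an objective, and research question f in section 3.2 asks how well the safety protocol detects and limits adverse events.

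**Working it through.** The plan gives no figure to reproduce here. The check has three parts.

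**1. Do follow-ups fall during therapy?**

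Inputs:
- therapy starts within two weeks of allocation (section 3.10), taken as day 0 to 14
- weekly sessions: RTM up to 5 (section 3.11.1); TF-CBT 12 in the simple-PTSD outline and up to 18 for complex PTSD (section 3.11.2)
- follow-up accepted up to ten working days before or after the due date (section 3.13), about 14 calendar days
- assumption: no missed session and no early ending

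Day of last session = start day + 7 × (n − 1):

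| Course | Last session |
|---|---|
| RTM, n = 5 | day 28 to 42 |
| TF-CBT, n = 12 | day 77 to 91 |
| TF-CBT, n = 18 | day 119 to 133 |

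- Week 6 is due on day 42, with a window of about day 28 to 56. All of it lies inside a 12- or 18-session TF-CBT course. An early week 6 questionnaire can also fall inside a full RTM course.
- Week 12 is due on day 84, with a window of about day 70 to 98. Every 18-session course is still running. A 12-session course ends within this window, so it may or may not be.

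**2. How much time would a message to the therapist save?**

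Let a questionnaire arrive t days after a session, with t uniform over the 7 days to the next one. Let review take r days (0 to 3, from the 72 hours in item 2.2.1), and let the therapist be told one day later.

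- Wait from receipt to next session: mean 7/2 = 3.5 days, maximum 7.
- Time saved = 6 − r − t when positive, otherwise 0.
- Mean saved = (6 − r)² / (2 × 7).
- r = 0: 36/14 = 2.57 days, maximum 6.
- r = 3: 9/14 = 0.64 days, maximum 3.
- r uniform on 0 to 3: 63/42 = 1.5 days.
- With r = 3, the rise is noted before the next session in 4/7 = 57% of cases. In the other 3/7 = 43% the session comes first.

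**3. Can a rise meet item 4.2 but not the in-session rule?**

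Item 4.1.1 compares with the previous session or baseline; item 4.2 compares with the previous follow-up or baseline. Take scores of 50 at baseline, 45 at week 6 and 55 at week 12:
- change since previous follow-up: 55 − 45 = +10, so item 4.2 is met
- if spread evenly over 6 sessions: 10/6 ≈ +1.7 per session, below 10
- change from baseline: 55 − 50 = +5, below 15

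Item 4.1.1 is not met. This cannot arise in the same way at week 6, where no earlier follow-up exists.

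**The case against.** Appendix 1 separates participants in therapy from participants in follow-up (items 3.1.1, 3.1.2 and 3.4.6). On that reading item 4.1 covers treatment, item 4.2 covers the period after it, and the GP or case worker is then the right recipient. People in therapy have other protection. The therapist takes a PCL-5 and CORE-10 at each session (item 4.1.1) and may escalate any concern without a score threshold (item 4.1). The unblinded researcher reports rises to the DMEC chair within three working days (item 4.1.2). The contact card lists Inspire's 24-hour helpline (item 3.1). Appendix 5 lists the therapist for the PCL-5 at weeks 6 and 12 but not later, and section 3.13 aligns collection with a therapy appointment where the two coincide, so the follow-up and in-session scores may often be the same. In the slow-rise example the therapist already holds the weekly scores. Up to 18 sessions applies to complex PTSD, and section 3.6 allows for 50% attrition in the comparison arm, so fewer people are exposed at week 12.

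Most of this stands, and it keeps the point minor. It does not close the gap. None of these provisions requires the accountable clinician to be told of a rise that the researcher notes between sessions. Item 4.1.2 informs an oversight committee, Appendix 5 concerns data source and entry, and the helpline depends on the participant calling. The phase distinction is not written into item 4.2, and item 2.2 blurs it.

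**Conclusion.** The point holds as a minor gap in the safety procedure. What remains exposed is mainly questionnaires completed by telephone or online between sessions, plus a slow rise between weeks 6 and 12 in someone still in therapy. For the first group the therapist's knowledge is delayed by about a week at most, provided no session is missed, and the participant is still contacted within six hours of the rise being noted. The time saved rests on assumed uniform arrival, weekly sessions and review within 72 hours. The protocol gives neither an alert rate nor the share of questionnaires completed between sessions, so the number of participants affected cannot be stated. No estimate, progression criterion or analysis depends on it.

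**What to change.** Add one sentence to item 4.2: if the participant is still in therapy, the unblinded researcher also informs the Inspire therapist within 24 hours of noting the rise and before the next session, and tells the participant so. This carries the existing rule in item 3.4.5 over to both arms. Reword item 2.2 so that weeks 6 and 12 are not presented as post-discharge for participants still in therapy.

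The cost is one extra message per alert. Blinding is unaffected: the unblinded researcher already acts under item 4.2, and the therapist knows the treatment. What the therapist then does clinically is outside this comment.

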5.0 Care escalation procedures in the case of serious adverse event

- **5.1** A serious Adverse Event that occurs during therapy will be investigated by Inspire according to their standardised clinical protocols and clinical governance framework
 - 5.1.1 The serious adverse event will be investigated by Inspire's clinical lead or delegated representative using Inspire's standardised SAE procedures template and within an agreed time-frame contingent on the nature and seriousness of the event.
 - 5.1.2 The completed investigation report will include recommendations, shared learning and corrective actions each to be completed within a specified time frame, presented to and signed off by the Inspire CEO Board alongside being shared with the DMEC chair for review.
- **5.2** A Serious Adverse Event that occurs following discharge from Inspire but whilst in the trial will be investigated by one of the study senior investigators (i.e. [name], [name], [name]) using Inspire's SAE investigational policies and procedures. Inspire protocols and timeframes will be used. The investigational report will be submitted to the DMEC chair.
- **5.3** The DMEC chair will be notified within 24 hrs of the research team being notified of all serious adverse events.

6.0 Ineligible participants

6.1 Inspire Associate Consultant Clinical Psychologists will determine whether each potential participant meets the inclusion and exclusion criteria. They will use Inspire's standardised risk assessment, escalation and management guidelines, and safeguarding policies and procedures to adhere to Inspire's clinical governance framework and ensure that:

6.2 Those considered ineligible for the study will be safely signposted to alternative specialist voluntary or statutory services

6.2.1 Those referred by MoD Aftercare Service will be discharged back to MoD Aftercare Service to put in place a bespoke care plan to safely meet their identified needs.

6.3. For anyone ineligible, but assessed as high risk, the GP will be contacted to, where necessary, mobilise crisis response and potential referral to NHS primary or secondary care.

6.3.1 If referred by MoD Aftercare – the field worker will also be mobilised to make follow up contact with the individual.

6.4 Where safeguarding and vulnerable adult's concerns are identified this will be escalated, acted on and reported to the relevant statutory body – safeguarding team.

6.5 For any individual deemed at immediate high risk and who is unable to keep themselves safe, emergency services will be contacted directly.

Appendix 2: Stakeholder involvement team

Overview and Core Values

The 'Involvement' aspect of the research will be facilitated by co-applicant [name]'s team.

We propose that the involvement of Service or ex-Service personnel and their families (hereafter referred to as 'The Involvement Team') would take the form of six two-hour meetings at appropriate points during the research.

 [name] would act as a Facilitator to the Involvement Team. She would also administer the remuneration (vouchers or cash) for Involvement Team members.

INVITING VETERANS TO BE PART OF 'INVOLVEMENT TEAM'

Recent (November 2017) direct discussions between the Facilitator, [name] (Customer Relations Manager, Inspire) and (Ret) Major [name], (Director of UDR and Royal Irish (HS) Armed Forces After Care) confirm that it be very straightforward to attract the following individuals to make up the 'Involvement Team':

- 4 to 5 veterans from NI (i.e. males and females who have experienced PTSD but who are no longer in need of active treatment for it); plus,

- one adult significant other of such individuals.

This process will be very straightforward because the Armed Forces After Care Service already has excellent direct links to families of veterans via the Case Workers who head up each of the four 'Field Teams' operating in different parts of NI: (N) Coleraine, (S) Craigavon, (E) Holywood and (W) Enniskillen. These Case Workers report directly to [name].

Our proposed approach to populating the Involvement Team is therefore to:

- Co-create, with [name], a brief (maximum two A4 pages) invitation pamphlet, for issue to the Case Workers in each of the four Field Teams. This pamphlet will summarise:
 - the overall purpose of the research overall;
 - the separate, but related, role of the Involvement Team;
 - the nature and duration of commitment;
 - the characteristics of the people we are looking for re the Involvement Team i.e. 4-5 veterans from NI (i.e. males and females who have experienced PTSD but who are no longer in need of active treatment for it); plus, one adult significant other of such individuals;
 - o key issues for Involvement Team members re confidentiality, security etc;
 - logistics / proposed meeting places / dates etc;
 - o remuneration arrangements (e.g. £50 voucher/cash etc) per person per meeting; and,
 - a very brief application form (to be submitted to [name] by a specified closing date) if someone is interested in being considered for membership of the Involvement Team.
- We will explain that places are limited (five veterans, five adult significant others). We would strive for at least one veteran per Field Team.
- The first applicant from each Field Team to meet the criteria, will be appointed to the Involvement Team.

- If oversubscribed, we will create a waiting list. This will also give us a pool of people to call upon in case any of the members of the Involvement Team needed to drop out at any stage during the project.
- All applications will be acknowledged and all applicants will be notified (within seven working days of the closing date) re whether they had 1) been appointed to the Involvement Team, 2) been added to the waiting list or 3) not met the criteria for either.

MEETING 1: ORIENTATION

Key meeting to establish trust and agree working arrangements.

Facilitator (and potentially [name] and [name] as well) will meet with the appointed members of the Involvement Team to:

- Confirm, agree and document core intention of involvement;
- Confirm the nature and duration of commitment;
- Confirm and agree core principles / values / ethos of all Involvement activities;
- Listen to and respond to needs of participants and significant others, including:
 - Concerns / fears / anxieties;
 - Creating and sustaining a sense of safety:
 - personnel involved;
 - locations;
 - language / terminology;
 - confidentiality;
 - personal data;
 - clear and timely information; and,
 - Confirming priorities within needs.
 - Motivation and personal goals re wishing to become part of the Involvement Team.
 - o Confirm the talents and skills amongst the members of the Involvement Team;
 - Confirm how the Facilitator might best serve the Involvement Team as the work proceeds.
- Agree how to proactively and appropriately resource members of Involvement Team;
- Agree logistics / meeting places etc and remuneration arrangements (e.g. £50 voucher/cash etc);
- Agree how and when records of meetings will be made, kept and distributed etc;
- Agree the scope of the remaining 5 Involvement meetings and how email and communication etc would operate between Involvement Team Members between meetings.

MEETING 2: DEVELOPING MATERIALS

Facilitate Involvement Team to review and/or develop and/or refine a range of research-related materials such as:

- Participant Information Sheets and consent forms;
- Documentation and approaches to raise awareness of the research;
- Video design and script to provide study information;

- Answers to FAQs for prospective research participants / significant others;
- Study information webpage design.

MEETING 3: CONDUCT OF RESEARCH

- Facilitate Involvement Team to identify how prospective research participants and / or their significant others could benefit from (or could have benefited from) further information on the research.
- Catalogue all such information needs identified.
- Address the information priorities during the meeting.
- Ensure that other information needs identified are delegated to, and addressed by, an appropriate member of the Involvement Team and / or wider Research Team.

MEETING 4: EVALUATION

- Facilitator to share key findings and conclusions from the research with the Involvement Team.
- Facilitate the Involvement Team to suggest how the findings and conclusions from the research could be:
 - communicated even more clearly; and,
 - Described / presented in an even more meaningful / impactful way.

MEETING 5: DISSEMINATION

- Facilitator to share with the Involvement Team the preliminary proposals for the dissemination of the research findings and conclusions.
- Facilitate the Involvement Team to provide their views on how the dissemination activities might be further optimised.

MEETING 6: REFLECTION

- Facilitator to facilitate the Involvement Team to reflect on their own journey of involvement during this research, noting:
 - What they found most helpful;
 - What they found least helpful;
 - What they would like to be done differently next time;
 - The single most important positive thing they consider they have gained from their experience; and,
 - Whether or not they would recommend being a member of the Involvement Team to others, and why.

